## INSTRUCTIONS

This template should be used by biomedical and social-behavioral researchers conducting research which subjects are assigned to receive one or more interventions so that the researchers can evaluate their effects. (e.g. clinical trials, CBT, Behavioral Modification studies, or randomized outcome studies)

## **1.0 Research Introduction**

### **1.1 Purpose/Specific Aims**

To characterize the effect of food supplemented with dietary fiber on glycemic response in humans

#### **A. Objectives**

To characterize the effect of food supplemented with dietary fiber on postprandial blood glucose levels. This pilot study will generate data to facilitate the development of a high dietary fiber dietary intervention for an upcoming study that aims at improving gut microbial profile and functions to improve glycemic control in patients with type 2 diabetes.

#### **B. Hypotheses / Research Question(s)**

We hypothesize that food supplemented with dietary fiber will reduce postprandial glycemic response as compared to a standard meal tolerance test (white bread with 50 g of available carbohydrates). Further, the impact of supplemented food, although with the same amount of dietary fiber, will vary due to differences in cooking procedures and serving temperatures.

#### **1.2 Research Significance (*Briefly describe the following in 500 words or less*):**

[figure not shown]
The gut ecosystem has now been regarded as the foundation for human health, with developing strategies to promote and maintain gut homeostasis as one of the key priorities in recent medical research. Dysbiosis (an imbalance of beneficial and detrimental microbes) has long been associated with metabolic diseases, notably obesity and type 2 diabetes. To date the mechanisms by which the gut microbiome impacts on host health have not been fully elucidated, but the literature points to short-chain fatty acid (SCFA) production from bacterial carbohydrate fermentation as a key microbial function that is essential for humans and the deficiency of which may lead to deleterious metabolic sequelae. SCFAs confer direct benefits to humans, e.g. butyrate is the primary energy substrate for colonocytes and a wide range of SCFAs function as signaling molecules that modulate inflammation and appetite regulation (1). SCFAs also impact on the gut ecosystem *per se*. By modulating gut luminal pH, SCFAs create a selective pressure against acid-intolerant bacteria (notably opportunistic pathogens) and therefore an acidity-driven shift in overall gut microbial structure (2).

Dietary fiber is the primary source of fermentable carbohydrates for the gut bacteria and thus dietary fiber supplementation is commonly used in microbiota-targeted dietary interventions. There is some evidence for increased dietary fiber intake to positively impact on metabolic outcomes in patients with type 2 diabetes (3, 4). A single dietary fiber type, however, is unlikely to confer universal benefits. The human gut microbiota is highly variable across individuals, with different capacities for fermenting dietary fiber of various physiochemical properties. Accordingly, it is logical to tailor microbiota-targeted dietary interventions based on each individuals gut microbial functions (a separate project that we are currently pursuing). From a population health perspective, dietary fiber fortification of everyday food products should consist of a broad range of dietary fiber types so that most individuals would be able to benefit from at least some of the ingredients.

We have developed two dietary fiber mixes, one consists of different bran as sources of insoluble dietary fiber (sorghum bran, corn bran, wheat bran and oat bran; Insoluble Mix) and the other one consists of two soluble dietary fiber (inulin and Fibersol-2®; Soluble Mix). The work proposed here will explore the effect of these two Mixes on glycemic response in human. This pilot study is part of the food/meal development for an upcoming study that will explore the effect of a gut microbiota-targeted dietary intervention program on glucose homeostasis in patients with type 2 diabetes.

#### **1.3 Research Design and Methods**

**OVERVIEW.** This is a pilot study to characterize the effect of food supplemented with dietary fiber on glycemic response in human. Participants will test 6 food items (plus a control food for comparison) with postprandial glycemic response monitored using a continuous glucose monitoring system. The study will be conducted at the Cook-Douglass Student Health Center and Harvest Café at New Jersey Institute for Food, Nutrition & Health (IFNH). There will be an eligibility screening and group assignment visit, and 14 food testing visits over 4 weeks (Figure 1).

**Figure 1. Study design.**

**RECRUITMENT.** Prospective participants will be recruited through advertisements on Rutgers University website and email lists (Attachment 3A), and flyers on the Rutgers University campuses (Attachment 3B). Interested individuals will be asked to contact the research team by phone, during which a research officer will provide an overview of the study and describe the broad selection criteria. Prospective participants will be invited to attend a screening visit to establish eligibility. The final selection will be contingent upon the individuals meeting all eligibility criteria and are deemed capable of complying with the protocol.

**ELIGIBILITY SCREENING.** Prospective participants will attend the eligibility screening visit after an overnight fast of at least 8 h. They will meet a member of the research team at IFNH, who will provide a detailed description of the study, including the rationale, aim, expected outcomes and significance of the research, the experimental procedures, what is required from the participants, and the benefits and risks associated with the study. Written informed consent (Attachment 4) will be obtained prior to the eligibility screening process. All information collected during the screening process will be documented in the screening checklist (Attachment 7). Specifically a Research Officer will record medical history and current medications and assess eligibility. Patients with type 2 diabetes who are receiving nutritional management and/or oral hypoglycemic medications may be eligible for the study, however those who are receiving insulin treatment or other injectable prescription medication will be excluded. A full list of inclusion and exclusion criteria is available in Section 4.2.

**GROUP ASSIGNMENT.** Upon confirmation of eligibility, the Research Officer will measure fasting blood glucose concentration (FBG) by performing a finger prick test (ACCU-CHEK® Aviva Plus, Roche Diabetes Care, Indianapolis, IN). Participants who are clinically diagnosed with impaired glucose tolerance or type 2 diabetes (diet-controlled and/or on oral hypoglycemic medications) will be assigned to the Prediabetes/Diabetes group irrespective of their finger prick test results. For participants who are not diagnosed with diabetes, those with FBG < 100 mg/dL will be assigned to the Non-Diabetes group, and those with FBG ≥ 100 mg/dL will be assigned to the Prediabetes/Diabetes group based on classification guidelines from the American Diabetes Association (5). Participants will also be asked to sign up for one of the testing panels: 1) Panel A will test one control food (white bread) and six fiber-supplemented food (dietary fiber mix in water, hot waffle, room temperature waffle, hot pancake, room temperature pancake and muffin); or 2) Panel B will test one control food (white bread) and six fiber-supplemented food (dietary fiber mix in water, sponge cake, crispbread, vegetable smoothie, fruit smoothie and muffin). Finally, the Research Officer will collect information to complete the participant profile, including anthropometry measurements (height and weight), and demographics and contact details.

The eligibility screening and group assignment visit will take approximately 1 h to complete.

**FOOD TESTING.** In the morning of each testing day, participants will attend IFNH between 8 and 10 am after an overnight fast of at least 8 h. They will be required to consume all the study food provided under supervision. The

amount of white bread to be consumed will contain 50 g of available carbohydrates (3-4 slices of bread), and the amount of fiber-supplemented food to be consumed will contain 60 g of dietary fiber mix (approximately 2 waffles, 2 pancakes, 2 slices of sponge cake, 2 serves of crispbread, 2 muffins or 300 ml of smoothies). Participants may leave the research facility after consuming the food, and they will be instructed to refrain from eating and drinking (except water) for the next 3 h. Each food will be tested twice over two consecutive days, with all testing to be completed in 4 weeks (Figure 1). Each food testing session will take approximately 30 min to complete.

[figure not shown]
Postprandial glycemic response will be assessed by changes in blood glucose concentrations, to be monitored using a continuous glucose monitoring system (CGM; FreeStyle Libre Pro, Abbott Diabetes Care, Alameda CA). On the first day of food testing, a sensor will be placed on the participant's arm by our Study Physician or other members of the research team trained by the sensor supplier (Abbott Diabetes Care). The sensor will stay on the participant's arm until the end of the study (the sensor will be replaced after 14 days as per manufacturer instructions). Participants will be asked not to take the sensor below 3 ft (1 m) of water and not to submerge the sensor in water for more than 30 min to prevent sensor malfunction. Should there is a need to take off the sensor prior to the intended wear duration, the sensor has fallen off or there is question about proper functioning of the sensors, participants should contact the research team and attend our facility to check the sensors and replace them if necessary. At completion of the last food testing, participants are required to return to IFNH for removal of the CGM sensor anytime between 3 h after the last food item is consumed and the end of the week.

**SAFETY MONITORING.** All food ingredients will be sourced from local commercial suppliers and the dietary fiber mixes will be prepared in-house at the Food Innovation Center of Rutgers University (a facility that operates under constant USDA inspection). The dietary fiber mixes will undergo microbial count testing at EMSL Analytical (Piscataway, NJ). All meals will be prepared at Harvest Café of IFNH where all managers are ServSafe certified. CGM data will be reviewed by our Research Physician who, with written consent from the participants, will communicate directly with their primary healthcare provider(s) should there be a need for medical care adjustment.

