##### **▪ Exclusion Criteria**

- Receiving insulin for diabetes treatment
- Receiving injectable prescription medicine
- Self-reported allergy or intolerance to any ingredients in the test food
- Any conditions deemed by the investigators that would prevent participation in the study, e.g. participation in past or active clinical research that may interfere with study outcomes, at the discretion of the investigators
- Any conditions deemed by the investigators that would compromise the individual's ability to complete the study, e.g. serious psychiatric conditions, at the discretion of the investigators

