#### **4.9 Risks to Subjects**

##### **A. Description of Subject Risk**

The finger prick test and the use of CGM sensor both involve piercing of the skin which may cause infection. However infection is rare.

Participants may experience gastrointestinal symptoms (e.g. bloating, flatulence, diarrhea, constipation or cramping) when they consume the fiber-supplemented test food. These discomforts are common, however, these discomforts are minor and they should not last longer than a few hours.

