##### **D. Assessment of Social Behavior Considerations**

- Reasonably Foreseeable Risks

N/A

- Risk Of Imposing An Intervention On Subject With Existing Condition

N/A

- Other Foreseeable Risks

N/A

- Observation And Sensitive Information

N/A

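### Participants on oral hypoglycemic drugs may leave each of 14 food sessions under a 3 h water-only instruction with no stated exception for treating low glucose, which is also missing from the listed risks

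*Combined protocol and SAP*

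**What the plan says.** **Who may enrol.** Section 1.3 (Eligibility screening) states: "Patients with type 2 diabetes who are receiving nutritional management and/or oral hypoglycemic medications may be eligible for the study". Insulin users are excluded, and section 4.2 D also excludes anyone "Receiving injectable prescription medicine". No oral drug class is excluded by name. Investigator discretion is the only other filter.

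**What happens at a session.** Section 1.3 sets "14 food testing visits over 4 weeks". Each participant arrives in the morning after fasting for at least 8 h, eats the assigned food under supervision, and may then leave the facility. From that point "they will be instructed to refrain from eating and drinking (except water) for the next 3 h". The instruction covers drinks as well as food, and the sentence has no exception.

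**What is eaten.** The white bread portion is defined by 50 g of available carbohydrate. For the other foods, "the amount of fiber-supplemented food to be consumed will contain 60 g of dietary fiber mix". One of these foods is the fiber mix in water.

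**What risks are named.** Section 4.9 A names infection from skin piercing, and it says: "Participants may experience gastrointestinal symptoms (e.g. bloating, flatulence, diarrhea, constipation or cramping) when they consume the fiber-supplemented test food". Section 4.9 E adds only advice on fluid intake to avoid constipation. Low glucose appears in neither.

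**What oversight exists.** Section 1.3 (Safety monitoring) says "CGM data will be reviewed by our Research Physician", with contact to the participant's own provider if care needs adjusting. Section 6.3 has safety information collected at visits or by phone, and it sets up a monitoring committee.

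**The concern.** The 3 h instruction is there to keep the glucose curve clean, and for most participants it is harmless. For someone taking a drug that lowers glucose, it is a standing order not to eat or drink anything but water. It is given just as the person becomes free to leave the site, and nothing in the protocol says what to do if symptoms of low glucose appear. The conscientious participant is the one most exposed, because following the rule exactly means waiting until the window ends. Full payment under section 4.8 B depends on successfully completing every session, which gives a further reason to comply.

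Participant safety is what is at stake. There is also a smaller analysis issue. If someone does eat to treat low glucose and nobody records it, the resulting rise could end up in the area under the curve for that food.

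**Working it through.** **1. Number of sessions.** Section 1.3 gives 6 test foods plus 1 control food, each tested twice: (6 + 1) × 2 = 14. This reproduces the protocol's own figure of 14 food testing visits. The instruction is given at every one of them.

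**2. Sequence within a session.** At least 8 h fasted, then one test food, then permission to leave, then 3 h of water only. The window starts with eating, so it is not an unbroken fast. Available carbohydrate is stated for white bread and not for the fiber foods, so the carbohydrate content of most sessions is unknown from the text.

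**3. Does any other provision lift the instruction or tell the participant how to treat symptoms?**
- *Exclusion of insulin and injectables (sections 1.3 and 4.2 D):* removes some drugs and leaves all oral drugs eligible.
- *Recording of medications at screening (1.3):* identifies who is medicated. No action for test days follows from it.
- *Investigator discretion (4.2 D):* could exclude a particular person, but gives no instruction to those enrolled.
- *Physician review of glucose data (1.3):* leads to contact with the provider. No review timing, glucose threshold or rescue step is given.
- *Glucose reports to participants (6.4 B):* emailed after all visits are finished.
- *Reporting of adverse events (6.3 C and D):* open at any time by phone, but it is described as reporting and does not give permission to treat.
- *Monitoring committee (6.3 A and F):* monthly updates and a meeting at least every 2 months, so it cannot act within one 3 h window.
- *Team meetings (6.1 B):* review non-compliance and record keeping afterwards.

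None of these lifts the instruction.

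**4. Can a frequency be computed?** It would need the number of participants on oral drugs, the drug classes, whether doses are taken on test mornings, and an event rate. The documents give none of these. The Prediabetes/Diabetes group also takes diet-controlled participants and undiagnosed people with fasting glucose of 100 mg/dL or more, so the number medicated could be zero. No rate or maximum is claimed.

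**5. Effect of a flagged curve.** Section 4.5 C plans 5 completers in each panel-by-group cell. With 2 tests per food, that is 5 × 2 = 10 curves per food per cell, so one curve affected by rescue intake is 1 of 10.

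**The case against.** The strongest reply is that the hazard is assumed. The documents report no low glucose on oral drugs and name no drug class. Participants have just eaten, and most of the test foods are ordinary items such as waffles, muffins or smoothies. The water-only rule is a routine standardization step, and nobody wrote that symptoms must go untreated. Participants can phone the team or withdraw. Consent includes a description of risks, and the consent form and screening checklist, neither of which was available for review, are natural places for such an instruction.

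Much of this stands. The size of the risk cannot be established, and the consent form may already contain the exception. It does not remove the gap in the protocol, which gives an explicit rule without the one exception that a medicated participant would need.

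Four stronger readings are tempting, and the documents do not support them:
- A reader might infer that the protocol directs participants to leave low glucose untreated. It is silent, and waiting out the window is the consequence of a literal reading only.
- A reader might add the windows up to 14 × 3 = 42 h, or count the 12 of 14 sessions with no stated carbohydrate, as a measure of danger. The first counts time under an instruction, spread over 4 weeks. The second treats unstated carbohydrate as low carbohydrate.
- A reader might take the N/A in section 4.9 D, on imposing an intervention on someone with an existing condition, as dismissal of medical risk. That item sits under social behavior considerations and shows nothing of the kind.
- A reader might infer that the food comparison will be biased. That needs low glucose to occur, intake to follow, no record of it, and a curve that covers it. Section 6.1 A does not state the time span of the curve.

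**Conclusion.** The point holds as a gap in sections 1.3 and 4.9. Participants on oral hypoglycemic drugs may leave each of 14 sessions, each begun after at least 8 h without food, under a 3 h water-only instruction with no exception for treating low glucose, and low glucose is not among the listed risks. This goes beyond missing detail, because following a stated rule exactly gives the worse safety outcome for a medicated participant whose glucose falls, for example after the fiber mix in water.

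It should be corrected, but its size is unknown. The conclusion rests on two assumptions: that at least one participant on a glucose-lowering drug enrols, and that low glucose can occur on that drug in this setting. It is confined to the protocol text. It does not show that harm is likely, or that the study's results would be invalid. The effect on the area under the curve is secondary and conditional.

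**What to change.** - In section 1.3 (Food testing), state that participants on glucose-lowering drugs may break the 3 h restriction to treat symptoms of low glucose, following instructions from the Study Physician, and should then contact the research team.
- Add low glucose to the risks in section 4.9 A and to the safety information already collected at each visit under sections 6.3 C and D.
- Confirm that the consent form says the same. If it already does, bring the protocol into line with it.
- Optional and minor: note the time of any rescue intake so that the affected curve can be identified.

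The cost is one sentence, one risk line and one item in an existing safety check. Sample size, visits, foods and outcome do not change. The downside is that a few curves may be affected in cells of 5 completers.

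### Because each food is tested on consecutive days, every second fiber test follows a fiber dose and the second bread test never does; the analysis should separate day 1 from day 2 in the bread contrast.

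*Combined protocol and SAP*

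**What the plan says.** Section 1.3 (Overview) sets the load: "Participants will test 6 food items (plus a control food for comparison", and "14 food testing visits over 4 weeks (Figure 1". The Food testing paragraph of the same section fixes the replication: "Each food will be tested twice over two consecutive days, with all testing to be completed in 4 weeks (Figure 1". It also fixes what is eaten. For the test items, "the amount of fiber-supplemented food to be consumed will contain 60 g of dietary fiber mix"; for the control, the "amount of white bread to be consumed will contain 50 g of available carbohydrates (3-4 slices of bread". Under Group assignment, "Panel A will test one control food (white bread) and six fiber-supplemented food", and Panel B has the same structure. Sessions start between 8 and 10 am after a fast of at least 8 h, and the only dietary rule after the meal covers the next 3 h.

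The hypothesis (Section 1.1 B) is that "food supplemented with dietary fiber will reduce postprandial glycemic response as compared to a standard meal tolerance test", the comparator being white bread. The data analysis plan (Section 6.1 A) is an ANOVA with Tukey's test on area under the curve (AUC). It has no term for first or second test day, food order or prior exposure, and does not say how a food's two tests are combined.

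The readable text gives no food order, no gap between pairs and no prior-day diet. Figure 1 may show order and gaps, but its image is not in the copy reviewed.

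**The concern.** The hypothesis is about the response to the meal just eaten. In the second test of a pair, a fiber food differs from bread in two ways at once: what is eaten that morning, and whether 60 g of fiber mix was eaten the morning before. If the earlier dose alters the next morning's glucose, part of the food-bread difference belongs to it and not to the test meal. The shift would have the same source for all six foods in a panel, so agreement among the foods would not be reassuring.

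The protocol's own rationale makes the question reasonable. Section 1.2 says "Dietary fiber is the primary source of fermentable carbohydrates for the gut bacteria" and describes fermentation products that act after the meal, and Section 1.4 links fiber regimens to better glucose control. Section 1.1 A says the results will feed the design of a later study in type 2 diabetes, so it matters which effect has been measured.

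**Working it through.** **The plan's own count.** 7 foods x 2 tests = 14 visits, as stated.

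**Interval within a pair.** Both sessions start between 8 and 10 am on consecutive days, so the second follows the first by 22 to 26 h.

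**Second-test exposure.** Fiber mix on the previous morning: 6 of 6 fiber foods, 0 of 1 for bread. This follows from the text alone. Figure 1 cannot change it, because the two tests of a food are fixed on consecutive days.

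**Effect on the contrast.** Let c be the change in AUC caused by a fiber dose the morning before (not given in the documents). Let p_F and p_B be the shares of fiber and bread *first* tests that follow a fiber morning. Averaging each food's two tests (also not stated in the plan):

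bias in (fiber minus bread) = c x (1 + p_F - p_B) / 2

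The calendars below are assumptions, chosen to cover the layouts that fit in 4 weeks.

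| Calendar | Position of bread | p_F | p_B | Bias |
|---|---|---|---|---|
| Free day between pairs (e.g. Mon-Tue, Thu-Fri) | any | 0 | 0 | 0.50c |
| Back to back within a week, 2-2-2-1 pairs | first of two | 2/6 | 0 | 0.67c |
| same | second of two | 2/6 | 1 | 0.17c |
| same | alone in the last week | 3/6 | 0 | 0.75c |
| 14 days in a row | first | 5/6 | 0 | 0.92c |
| same | middle | 4/6 | 1 | 0.33c |
| same | last | 5/6 | 1 | 0.42c |

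The bias is zero in none of these layouts unless c = 0.

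**Illustration, assuming c between 0 and 15% of AUC.**
- Free days: 0.50 x 15% = 7.5%, so 0 to 7.5% of AUC.
- Back to back: at c = 15%, from 0.167 x 15% = 2.5% to 0.75 x 15% = 11.25%, depending on where bread falls.
- 14 days in a row: at c = 15%, from 0.333 x 15% = 5% to 0.917 x 15% = 13.75%.

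At c = 0 all are zero.

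**Can the data show it?** With a free day between pairs, no first test follows a fiber morning. Write d for any general change from day 1 to day 2. The expected day-2 minus day-1 change is d + c for fiber foods and d for bread, and the difference is c. This needs d to be the same for both, and no effect lasting long enough to reach the next pair.

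**Contrasts between fiber foods.** All six have the same exposure at the second test, so with free days c cancels. Without free days, first tests can differ according to which food came before.

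**The case against.** The strongest objection is that nothing in the documents shows a next-morning effect of a single dose. Section 1.4 reports 3-month regimens, with outcomes such as HbA1c, microbial structure and fecal pH; Section 1.2 describes fermentation in general terms. That stands. A reader might infer that the bread contrast is shown to be biased, and in favor of fiber. The documents support neither: c may be zero and its sign is not given. What they establish is that the second-day contrast cannot identify the meal effect by itself.

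A reader might also infer that the duplicate tests cannot expose the problem because the second one carries it. That is not so. With free days between pairs, comparing the change across days in fiber foods with that in bread estimates c from data the study already plans to collect. The plan simply does not include that comparison.

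Nor is a single bias fraction justified. A fraction near one half for every calendar would need a randomized food order, and the readable text states no order; by bread's position the fraction runs from 0.17 to 0.92.

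Finally, this is a pilot without a power calculation (Section 1.5), and testing in consecutive pairs is a defensible logistical choice. That limits how much redesign is warranted, but a change of analysis wording remains worthwhile.

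**Conclusion.** The point holds as a limit on what the design can identify. On day 2, food type and prior-morning fiber are fully confounded in the food-versus-bread contrast, and the planned ANOVA does not separate the days. If the two days are averaged, the bias is 0.50c with free days between pairs, 0.17c to 0.75c with back-to-back pairs, and 0.33c to 0.92c over 14 straight days. With free days and an assumed c of 0-15%, it is 0-7.5% of AUC. These figures rest on three assumptions: the averaging, the calendars, and an effect confined to the next morning and equal for all foods. The hypothesis about cooking procedure and serving temperature is largely untouched.

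**What to change.** Keep the paired layout and make two changes.

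1. **Section 1.3:** state at least one free day between pairs. Seven pairs and six single free days take 7 x 2 + 6 = 20 days, within 28; two pairs a week on weekdays also fits. If Figure 1 already shows this, the text need only say so.
2. **Section 6.1 A:** pre-specify the food-versus-bread contrast on first-day tests alongside the two-day mean. Add a day-by-food comparison (fiber versus bread) of the day-2 minus day-1 change as the check for carry-over. Credit the two-day result to the test meal only if the day-1 result agrees, judged on the estimates and their intervals.

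**Cost.** Visits, portions and sensor use are unchanged. The day-1 contrast uses half the replicates: if test errors are independent with variance s², the variance of one food minus bread within a participant rises from s²/2 + s²/2 = s² to 2s², so the standard error grows by a factor of √2, about 1.4.

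The carry-over check has low power. Averaging over six fiber foods, its variance per participant is 2s²/6 + 2s² = 2.33s². The standard error is √(2.33/5) = 0.68s with the 5 completers of one cell and √(2.33/20) = 0.34s with all 20. A non-significant check therefore does not show that carry-over is absent.

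Putting two different foods in each two-day block, in a cycle, would let bread also follow a fiber food, but it should not be the first choice. With free days between blocks, the fiber food placed after bread would have 0 of 2 tests after fiber and the other five 1 of 2. That moves the imbalance into the comparison between fiber foods.
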